1.2. Schema

A summary of the overall study design is presented in [Figure 1](#).

Figure 1 Study Design Schematic**1.3. Schedule of Activities (SoA)**

- Screening procedures may be done over more than 1 visit but must all be completed within 28 days prior to the first dose of study intervention.
- The following demographic parameters will be captured: year of birth, sex, race, and ethnicity.
- Medical/medication/family history will be assessed as related to the inclusion/exclusion criteria.

Screening Visit

Procedure	Screening (up to 28 days before Day 1)
Outpatient visit	X
Informed consent	X
Inclusion and exclusion criteria	X
Demography	X
Full physical examination including height and weight ¹	X
Laboratory assessments (hematology, chemistry, urinalysis)	X
12-lead electrocardiogram	X
Vital sign measurements	X
Medication/drug/alcohol history	X
Past and current medical conditions	X
Columbia Suicide Severity Rating Scale	X
Serum pregnancy test	X
Follicle-stimulating hormone (as needed, to confirm postmenopausal status)	X
Drug, alcohol, and cotinine screen	X
HIV, Hepatitis B and C screening	X

HIV = human immunodeficiency virus.

1 A full physical examination will include at a minimum, assessments of the skin, cardiovascular, respiratory, gastrointestinal, and neurological systems.

Procedure	Period 1		W	Period 2			Period 3							Follow-up				Notes	
	Day -1	Day 1-5	Day 6-9	Day 1-5	Day 6	Day 7	Day 1	Day 2	Day 3	Day 4	Day 5	Day 6	Day 7	Day 8	Day 9	Day 10 ¹	Day 11		
Admit to clinic	X																		
Discharge from clinic																		X	
Brief physical examination	X																X		A brief physical examination will include, at a minimum, assessments of the skin, lungs, cardiovascular system, and abdomen (liver and spleen).
Vital sign measurements	X	X		X	X	X	X	X	X	X	X	X	X	X	X	X	X	X	
12-Lead ECG	X	D1 and D5		D1 and D5			X			X	X		X				X		All ECGs in Period 1-3 will be pre-dose, post-dose at 2 hours, and post-dose at 4 hours. The predose ECGs on Day 1 of both Period 1 and Period 2 will be taken in triplicate.
Drug, alcohol, and cotinine screen	X																		See Appendix 2 for specific tests to be performed.
Laboratory assessments (hematology, chemistry, urinalysis)	X		D9			X				X			X				X		See Appendix 2 for specific tests to be performed.
Pregnancy test	X																X		
Columbia Suicide Severity Rating Scale				D1									X						
Genetic sample	X																		

Procedure	Period 1		W	Period 2			Period 3							Follow-up				Notes

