2.2. Study Objective(s) and Endpoint(s)

Ob	jectives	En	dpoints
Pri	Primary Objectives		mary Endpoints
•	To assess the effect of GSK3640254 on the steady state PK of DTG under fed conditions in healthy participants	•	Area under the plasma concentration-time curve (AUC) from time 0 to the end of the dosing interval at steady state [AUC(0- τ)], maximum observed concentration (Cmax), and plasma concentration at the end of the dosing interval (C τ) for DTG
•	To assess the effect of DTG on the steady state PK of GSK3640254 under fed conditions in healthy participants	•	AUC(0- τ), Cmax, and C τ for GSK3640254
Se	condary Objectives	Se	condary Endpoints
•	To assess the safety and tolerability of GSK3640254 and DTG administered alone and when given in combination in healthy participants	•	Safety and tolerability parameters for adverse events (AEs)/serious AEs (SAEs), observed and change from baseline clinical laboratory assessments, electrocardiograms (ECGs), and vital sign measurements
•	To characterize the steady state PK of GSK3640254 alone and when given in combination with DTG under fed conditions in healthy participants	•	Time of maximum observed concentration (Tmax) and apparent terminal phase half-life (t1/2) for GSK3640254
•	To characterize the steady state PK of DTG alone and when given in combination with GSK3640254 under fed conditions in healthy participants	•	Tmax and t1/2 for DTG

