5.2. Baseline Definitions

For all endpoints (except as noted in baseline definitions), the baseline value will be the latest pre-dose assessment with a non-missing value, including those from unscheduled visits. If time is not collected, Day 1 assessments are assumed to be taken prior to first dose and used as baseline. Baseline definitions in the tables below are applicable to each period.

Parameter	Study Asses	Baseline Used in			
	Screening	Day -1	Day 1 (Pre-Dose)	Data Display	
Safety					
Vital Sign	X	X	Х	Day 1 (Pre-Dose)	
12-Lead ECG	Х	Х	Х	Day 1 (Pre-Dose)[1]	

^[1] Baseline for 12-lead ECGs are applied to each period. The average (for quantitative assessments) or the worst case (for interpretation) of the predose triplicate assessments on Day 1 of Period 1 will be used as the baseline for Period 1. The average (for quantitative assessments) or the worst case (for interpretation) of the predose triplicate assessments on Day 1 of Period 2 will be used as the baseline for Period 2.

Parameter	Study A	Baseline Used in		
	Day -1	Period 1 Day 9	Period 2 Day 7	Data Display
Safety				
Hematology, Clinical Chemistry, Urinalysis	Х	X	X	Day -1 for Period 1; Period 1 Day 9 for Period 2; Period 2 Day 7 for Period 3

Unless otherwise stated, if baseline data is missing no derivation will be performed and baseline will be set to missing.

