10. APPENDICES

10.1. Appendix 1: Schedule of Activities

10.1.1. Protocol Defined Schedule of Events

Screening Visit

Procedure	Screening (up to 28 days before Day 1)
Outpatient visit	Х
Informed consent	X
Inclusion and exclusion criteria	X
Demography	X
Full physical examination including height and weight ¹	X
Laboratory assessments (hematology, chemistry, urinalysis)	X
12-lead electrocardiogram	X
Vital sign measurements	X
Medication/drug/alcohol history	Х
Past and current medical conditions	Х
Columbia Suicide Severity Rating Scale	Х
Serum pregnancy test	X
Follicle-stimulating hormone (as needed, to confirm postmenopausal status)	Χ
Drug, alcohol, and cotinine screen	Χ
HIV, Hepatitis B and C screening	Х

HIV = human immunodeficiency virus.

¹ A full physical examination will include at a minimum, assessments of the skin, cardiovascular, respiratory, gastrointestinal, and neurological systems.

Time and Events Table

	Peri	od 1	W	P	Period 2	2			ſ	Period 3	3				Follo	w-up		Notes
Procedure	Day -1	Day 1-5	Day 6-9	Day 1-5	Day 6	Day 7	Day 1	Day 2	Day 3	Day 4	Day 5	Day 6	Day 7	Day 8	Day 9	Day 10 ¹	Day 11	
Admit to clinic	Χ																	
Discharge from clinic																	Χ	
Brief physical examination	Х															Х		A brief physical examination will include, at a minimum, assessments of the skin, lungs, cardiovascular system, and abdomen (liver and spleen).
Vital sign measurements	Х	Х		Х	Х	Х	Х	Х	Х	Х	Х	Х	Х	Х	Х	Х	Х	
12-Lead ECG	х	D1 and D5		D1 and D5			Х			Х	Х		Х			х		All ECGs in Period 1-3 will be pre-dose, post-dose at 2 hours, and post-dose at 4 hours. The predose ECGs on Day 1 of both Period 1 and Period 2 will be taken in triplicate.
Drug, alcohol, and cotinine screen	Χ																	See Protocol Appendix 2 for specific tests to be performed.
Laboratory assessments (hematology, chemistry, urinalysis)	Х		D9			Х				Х			Х			Х		See Protocol Appendix 2 for specific tests to be performed.
Pregnancy test	Х															Х		
Columbia Suicide Severity Rating Scale				D1									Х					
Genetic sample	Х																	

	Peri	od 1	W	F	Period 2	!			I	Period :	3				Follo	w-up		Notes
Procedure	Day -1	Day 1-5	Day 6-9	Day 1-5	Day 6	Day 7	Day 1	Day 2	Day 3	Day 4	Day 5	Day 6	Day 7	Day 8	Day 9	Day 10 ¹	Day 11	
Study intervention: Dolutegravir 50 mg		Х					Χ	Χ	Χ	Χ	Χ	Χ	Χ					
Study intervention: GSK3640254 200 mg				Х	Х	Х	Х	Х	Х	Х	Х	Х	Х					

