DTG trough PK sampling		D2-4						Х	Х	Х	Х	Х						Blood collection for DTG trough PK samples will be collected on Days 2 through 4 in Period 1, Days 2 through 6 in Period 3.
DTG serial PK sampling		D5	D6-8										Х	х	х	х		Blood collection for PK analysis of DTG will be collected predose, and after dosing at 1, 1.5, 2, 3, 3.5, 4, 4.5, 5, 6, 8, 12, 24, 48, and 72 hours relative to Day 5 dosing in Period 1, and relative to Day 7 dosing in Period 3.
GSK3640254 trough PK sampling				D 4-5	х					Х	Х	х						Blood collection for GSK3640254 trough PK samples will be collected on, Days 4 through 6 in Period 2; and Days 4 through 6 in Period 3.

	Peri	od 1	W	Р	eriod 2				F	Period :	3				Follo	w-up		Notes
Procedure	Day -1	Day 1-5	Day 6-9	Day 1-5	Day 6	Day 7	Day 1	Day 2	Day 3	Day 4	Day 5	Day 6	Day 7	Day 8	Day 9	Day 10 ¹	Day 11	
GSK3640254 serial PK sampling						Х	Х						Х	X	X	X	X	Relative to Day 7 dosing in Period 2, blood for PK analysis of GSK3640254 will be collected predose, and after dosing at 1, 2, 2.5, 3, 3.5, 4, 4.5, 5, 6, 8, 12, and 24 hours. Relative to Day 7 dosing in Period 3, the PK samples will be collected at predose, and after dosing at 1, 2, 2.5, 3, 3.5, 4, 4.5, 5, 6, 8, 12, 24, 48, 72, and 96 hours.
AE review												==→						
SAE review	←									==>								
Concomitant medication review	ew							=>										

AE = adverse event; D = Day; DTG = dolutegravir; ECG = electrocardiogram; PK = pharmacokinetic; SAE = serious adverse event; W = washout.

1 Evaluations scheduled for Day 10 in Period 3 will also be performed for participants who discontinue early.

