10.2. Appendix 2: Study Phases and Treatment Emergent Adverse Events

10.2.1. Study Phases

Assessments and events will be classified according to the time of occurrence relative to study treatment start date(/time) and stop date(/time).

Study Phase	Definition
Pre-Treatment	Date and Time ≤ Study Treatment Start Date and Time
On-Treatment	Study Treatment Start Date and Time < Date and Time ≤ Study Treatment Stop Date and Time + 5 days
Post-Treatment	Date and Time > Study Treatment Stop Date and Time + 5 days

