10.4. Appendix 4: Derived and Transformed Data

10.4.1. General

Multiple Measurements at One Analysis Time Point

- Mean of the measurements will be calculated and used in any derivation of summary statistics but if listed, all data will be presented.
- The worst finding/interpretation associated with multiple measurements as the finding/interpretation for that time point.
- Participants having both High and Low values for Normal Ranges at any post-baseline visit for safety parameters will be counted in both the High and Low categories of "Any visit post-baseline" row of related summary tables. This will also be applicable to relevant Potential Clinical Importance summary tables.

Study Day

- Calculated as the number of days from First Dose Date in Period 1:
 - Ref Date = Missing
- → Study Day = Missing
- Ref Date < First Dose Date in Period 1 → Study Day = Ref Date First Dose Date
- Ref Date >= First Dose Date in Period 1 → Study Day = Ref Date (First Dose Date in Period 1) +

Period Day

- Calculated as the number of days from First Dose Date for the respective period:
 - Ref Date = Missing
- → Study Day = Missing
- Ref Date < First Dose Date in Period 1 → Study Day = Ref Date First Dose Date
- First Dose Date in Period 1 <= Ref Date < First Dose Date in Period 2 → Study Day = Ref Date –
 (First Dose Date in Period 1) + 1
- First Dose Date in Period 2 <= Ref Date < First Dose Date in Period 3 → Study Day = Ref Date –
 (First Dose Date in Period 2) + 1
- Ref Date >= First Dose Date in Period 3 → Study Day = Ref Date (First Dose Date in Period 3) +

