10.9.5. Safety Tables

Safety:	Safety: Tables						
No.	Population	IDSL / Example Shell	Title	Programming Notes	Deliverable		
Advers	e Events (AEs)						
2.1.	Safety	AE1CP	Summary of Adverse Events by System Organ Class and Preferred Term		SAC		
2.2.	Safety	AE1CP	Summary of Drug-Related Adverse Events by System Organ Class and Preferred Term		SAC		
2.3.	Safety	AE3	Summary of Common (>=5%) Adverse Events by Overall Frequency		SAC		
2.4.	Safety	AE15	Summary of Common (>=5%) Non-serious Adverse Events by System Organ Class and Preferred Term (Number of Subjects and Occurrences)		SAC		
2.5.	Safety	AE16	Summary of Serious Adverse Events by System Organ Class and Preferred Term (Number of Subjects and Occurrences)		SAC		
2.6.	Safety	AE5A	Summary of Adverse Events by System Organ Class and Preferred Term and Maximum Intensity		SAC		
Laborat	tory: Chemistry	/					
2.7.	Safety	LB1	Summary of Clinical Chemistry Changes from Baseline		SAC		
2.8.	Safety	LB16	Summary of Clinical Chemistry Results by Maximum Grade Increase Post-Baseline Relative to Baseline		SAC		
Laborat	tory: Hematolo	gy					
2.9.	Safety	LB1	Summary of Hematology Changes from Baseline		SAC		
2.10.	Safety	LB16	Summary of Hematology Results by Maximum Grade Increase Post-Baseline Relative to Baseline		SAC		

Safety:	Tables				
No.	Population	IDSL / Example Shell	Title	Programming Notes	Deliverable
Labora	tory: Urinalysis	S			•
2.11.	Safety	UR3	Summary of Urinalysis Dipstick Results		SAC
2.12.	Safety	LB1	Summary of Urine Concentration Changes from Baseline		SAC
2.13.	Safety	LB16	Summary of Urinalysis by Maximum Grade Increase Post- Baseline Relative to Baseline		SAC
ECG					
2.14.	Safety	EG1	Summary of ECG Findings		SAC
2.15.	Safety	EG2	Summary of ECG Changes from Baseline		SAC
2.16.	Safety	EG10	Summary of Maximum QTc Values Post-Baseline Relative to Baseline by Category		SAC
2.17.	Safety	EG11	Summary of Maximum Increase in QTc Values Post-Baseline Relative to Baseline by Category		SAC
Vital Si	gns				
2.18.	Safety	VS1	Summary of Vital Sign Changes from Baseline		SAC
C-SSR	S				
2.19.	Safety	CSSRS4	Listing of C-SSRS Suicidal Ideation and Behavior Data		SAC

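### The maximum-QTc tables draw on 12 scheduled post-baseline ECGs for the combination but 5 for each drug alone, which biases the combination column upward in expectation

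*SAP*

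**What the plan says.** SAP Section 10.9.5 lists Table 2.16 (maximum post-baseline QTc by category) and Table 2.17, "Summary of Maximum Increase in QTc Values Post-Baseline Relative to Baseline by Category". The programming notes for both are empty, so neither is limited to particular days. SAP Section 10.3.2 also lets unscheduled readings count toward worst-case values. The categories in SAP Section 10.7.1 include absolute QTc above 450, 480 and 500 msec and increases above 30 and 60 msec.

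The ECG row of the schedule (Protocol Section 1.3, repeated in SAP Section 10.1.1) marks Days 1 and 5 in Periods 1 and 2. In Period 3 it marks Days 1, 4, 5 and 7 and one follow-up day. The note reads: "All ECGs in Period 1-3 will be pre-dose, post-dose at 2 hours, and post-dose at 4 hours".

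On baseline, SAP Section 5.2 says "Baseline definitions in the tables below are applicable to each period", and for ECGs it uses the Day 1 pre-dose value. Replication differs by period: "The predose ECGs on Day 1 of both Period 1 and Period 2 will be taken in triplicate". Protocol Section 8.2.3 makes ECGs at all other time points single.

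The related secondary objective is "To assess the safety and tolerability of GSK3640254 and DTG administered alone and when given in combination in healthy participants".

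**The concern.** The maximum of several noisy readings rises with the number of readings. A participant measured 12 times on the combination has more chances of a high value than the same participant measured 5 times on one drug. Columns built this way do not measure the same quantity, and the difference favours finding more on the combination.

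Protocol Section 2.3 names QTc prolongation as a major risk of GSK3640254, and the secondary objective covers each drug alone and the two together. With about 16 participants and no formal safety testing (Protocol Section 9.4.2), readers will go by raw counts, where one or two extra participants in a category are noticeable.

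**Working it through.** **1. Count of scheduled post-baseline ECGs** (three time points per dosing day, less the Day 1 pre-dose baseline)

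- Period 1: 2 × 3 − 1 = 5
- Period 2: 2 × 3 − 1 = 5
- Period 3, dosing days: 4 × 3 − 1 = 11
- Period 3, Day 10: 1 more, giving 12

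Day 10 belongs to Period 3 on three grounds. The schedule footnote places it there: "Evaluations scheduled for Day 10 in Period 3 will also be performed for participants who discontinue early". The period-day rule in SAP Section 10.4.1 assigns every date with "Ref Date >= First Dose Date in Period 3" to that period. The on-treatment window in SAP Section 10.2.1, "Study Treatment Start Date and Time < Date and Time ≤ Study Treatment Stop Date and Time + 5 days", runs to Day 7 + 5 = Day 12. Anyone who excludes Day 10 has 11 against 5.

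**2. Expected maximum with no drug effect.** The plan states no figure to reproduce. For k independent normal readings with SD s, the expected maximum is s × e(k), where e(k) = ∫ x·k·φ(x)·Φ(x)^(k−1) dx. Numerically, e(5) = 1.163, e(11) = 1.586 and e(12) = 1.629. The gap is 0.466 s for 12 against 5, and 0.423 s for 11 against 5. The documents do not give s, so a range is assumed:

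- s = 6: 0.466 × 6 = 2.8 msec
- s = 8: 0.466 × 8 = 3.7 msec
- s = 10: 0.466 × 10 = 4.7 msec

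With a correlation of 0.5 between readings, the gap is multiplied by √(1 − 0.5) = 0.71. At s = 10 it falls from 4.7 to 3.3 msec.

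**3. Chance of an increase above 30 msec (Table 2.17).** P = ∫ f(b)·[1 − Φ((30 + b)/s)^k] db, where f is the density of the baseline error b. Its variance is s²/3 for a triplicate mean and s² for a single ECG.

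| s (msec) | 5 readings, triplicate | 12 readings, triplicate | 5 readings, single | 12 readings, single |
|---|---|---|---|---|
| 6 | about 0% | about 0% | 0.1% | 0.2% |
| 8 | 0.3% | 0.7% | 1.7% | 3.4% |
| 10 | 2.2% | 4.9% | 6.5% | 11.7% |

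The first two columns isolate the reading count. The first and last compare a single-drug period with Period 3 as scheduled. The first and third show what remains if time points are matched but the Period 3 baseline stays single.

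**4. What 16 participants would show, from the count alone.** The chance that at least one exceeds 30 msec is 1 − (1 − p)^16. At s = 8 it is 5% for 5 readings and 10% for 12; at s = 10 it is 30% and 56%. In null trials comparing the combination with one single-drug period, the counts above 30 msec tie in 99.8%, 86% and 41% of trials at s = 6, 8 and 10. The combination has the higher count in about 10% at s = 8 and 44% at s = 10.

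**5. Absolute values (Table 2.16).** Assuming also a mean QTcF of 410 msec and a between-participant SD of 15 msec, the expected number of 16 above 450 msec is 0.44 for 5 readings against 0.69 for 12 at s = 8. At s = 10 it is 0.69 against 1.13. Baseline replication plays no part here.

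**The case against.** A reader might infer that the combination will look worse in these tables, and that the excess could not be separated from an interaction. The documents support neither.

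- **The bias is an expectation.** The tables show categories, not mean maxima. At an SD of 6 msec or below the count effect is negligible, and at 8 msec most null trials tie. The SD is an assumption, and positive correlation between readings shrinks the gap. This stands.
- **Other displays allow a partial check.** Figure 2.1 shows mean QTcF change by time point and treatment, and Table 2.15 summarises changes from baseline; neither takes a maximum. Listing 28 gives all ECG values for anyone with a value of potential clinical importance, so the day of an exceedance can be found. This stands, although these displays do not replace the categorical tables.
- **The layout is inferred.** Neither title says by treatment, and the IDSL shells are not in the documents. The treatment display order in SAP Section 5.1 and the period-specific baselines make that layout the natural reading.
- **A worst-case table is meant to use every reading.** This is fair for outlier screening and is a reason to keep the existing tables. It does not make their columns comparable.
- **Matching time points does not fully repair Table 2.17.** At SD 10 msec, 6.5% against 2.2% remains because of the single Period 3 baseline. That baseline is also taken without a GSK3640254 washout (Protocol Section 4.3), so if the drug affects QTc, Table 2.17 could be pulled the other way. This stands and shapes the fix.

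**Conclusion.** The imbalance of 12 readings (or 11) against 5 follows from the plan's own schedule, baseline and period rules, and nothing in Tables 2.16 and 2.17 offsets it. If these are shown by treatment, the combination column is biased upward in expectation with no drug effect. The visible size depends on a QTcF SD that the documents do not give: negligible in the category counts at 6 msec or below, and roughly a doubling of a small probability at 8 to 10 msec from the reading count alone. In Table 2.17 the single Period 3 baseline adds to this. These figures assume independent normal readings. The point concerns comparability between columns; it does not show that an apparent excess is certain or impossible to investigate.

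**What to change.** - Keep Tables 2.16 and 2.17 on all readings for outlier screening, and show the number of scheduled post-baseline readings per treatment (5, 5 and 12).
- Add a version of each restricted to the time points common to all three periods: Day 1 at 2 h and 4 h; Day 5 pre-dose, 2 h and 4 h. Each treatment then has 5 readings. State that any comparison of the combination with each drug alone uses these versions.
- Footnote Table 2.17, in both versions, that the Period 3 baseline is a single ECG taken during continued GSK3640254 dosing, so matching time points does not make the increase categories fully comparable. The matched Table 2.16 is the cleaner comparison.

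The cost is two extra tables and some annotation, from data already collected. Period 3 Days 4, 7 and 10 are left out of the matched versions only.

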10.9.6. Safety Figures

Safety:	Safety: Tables						
No.	Population	IDSL / Example Shell	Title	Programming Notes	Deliverable		
ECG							
2.1.	Safety	EG9	Mean (95% CI) Change from Baseline in QTcF Interval by Timepoint and Treatment		SAC		

10.9.7. Pharmacokinetic Tables

Pharmacokinetic: Tables								
No.	Population	IDSL / Example Shell	Title	Programming Notes	Deliverable			
PK Cor	ncentration Data							
3.1.	PK Concentration	PKCT1	Summary of DTG Plasma Pharmacokinetic Concentration-Time Data by Treatment		SAC			
3.2.	PK Concentration	PKCT1	Summary of GSK3640254 Plasma Pharmacokinetic Concentration-Time Data by Treatment		SAC			
3.3.	PK Concentration	PKCT1	Summary of Predose (trough) DTG Plasma Concentrations by Treatment		SAC			
3.4.	PK Concentration	PKCT1	Summary of Predose (trough) GSK3640254 Plasma Concentrations by Treatment		SAC			
PK Der	PK Derived Parameters							
3.5.	PK Parameter	PKPT4	Summary of Derived DTG Plasma Pharmacokinetic Parameters (Non-Transformed) Based on Actual Time by Treatment	Parameters with units	SAC			

Pharma	Pharmacokinetic: Tables						
No.	Population	IDSL / Example Shell	Title	Programming Notes	Deliverable		
3.6.	PK Parameter	PKPT4	Summary of Derived DTG Plasma Pharmacokinetic Parameters (Ln-Transformed) Based on Actual Time by Treatment	Parameters with units	SAC		
3.7.	PK Parameter	PKPT4	Summary of Derived GSK3640254 Plasma Pharmacokinetic Parameters (Non-Transformed) Based on Actual Time by Treatment	Parameters with units - use ug instead of ng where applicable for GSK3640254	SAC		
3.8.	PK Parameter	PKPT4	Summary of Derived GSK3640254 Plasma Pharmacokinetic Parameters (Ln-Transformed) Based on Actual Time by Treatment	Parameters with units - use ug instead of ng where applicable for GSK3640254	SAC		
PK Ana	alysis Tables						
3.9.	PK Parameter	PKPT3	Statistical Analysis of DTG Plasma Pharmacokinetic Parameters	AUC(0-т), Ст, and Cmax	SAC		
3.10.	PK Parameter	PKPT3	Statistical Analysis of GSK3640254 Plasma Pharmacokinetic Parameters	AUC(0-т), Ст, and Cmax	SAC		

10.9.8. Pharmacokinetic Figures

Pharm	acokinetic: Figu	res			
No.	Population	IDSL / Example Shell	Title	Programming Notes	Deliverable [Priority]
Individ	ual Concentration	on Plots			
3.1.	PK Concentration	PKCF1	Individual DTG Plasma Concentration-Time Plots by Participant (Linear and Semi-Logarithmic)	Paginate by Participant Dashed line represents the LLQ Treatments Overlaid	SAC
3.2.	PK Concentration	PKCF1	Individual GSK3640254 Plasma Concentration-Time Plots by Participant (Linear and Semi-Logarithmic)	Paginate by Participant Dashed line represents the LLQ Treatments Overlaid	SAC
3.3.	PK Concentration	PKCF1	Individual DTG Plasma Concentration-Time Plots by Treatment (Linear and Semi-Logarithmic)	Paginate by Treatment Dashed line represents the LLQ Participants Overlaid	SAC
3.4.	PK Concentration	PKCF1	Individual GSK3640254 Plasma Concentration-Time Plots by Treatment (Linear and Semi-Logarithmic)	Paginate by Treatment Dashed line represents the LLQ Participants Overlaid	SAC
Mean /	Median Concen	tration Plots			
3.5.	PK Concentration	PKCF2	Mean (± Standard Deviation) DTG Plasma Concentration-Time Plots by Treatment (Linear and Semi-Logarithmic)	Treatments Overlaid	SAC
3.6.	PK Concentration	PKCF2	Mean (± Standard Deviation) GSK3640254 Plasma Concentration-Time Plots by Treatment (Linear and Semi- Logarithmic)	Treatments Overlaid	SAC
3.7.	PK Concentration	PKCF3	Median (Range) DTG Plasma Concentration-Time Plots by Treatment (Linear and Semi-Logarithmic)	Treatments Overlaid	SAC

Pharma	Pharmacokinetic: Figures						
No.	Population	IDSL / Example Shell	Title	Programming Notes	Deliverable [Priority]		
3.8.	PK Concentration	PKCF3	Median (Range) GSK3640254 Plasma Concentration-Time Plots by Treatment (Linear and Semi-Logarithmic)	Treatments Overlaid	SAC		
3.9.	PK Concentration	PKCF2	Mean (± Standard Deviation) Predose (Trough) DTG Plasma Concentration Plots by Treatment (Linear and Semi- Logarithmic)		SAC		
3.10.	PK Concentration	PKCF2	Mean (± Standard Deviation) Predose (Trough) GSK3640254 Plasma Concentration-Time Plots by Treatment (Linear and Semi-Logarithmic)		SAC		

